**Table 17: Baseline Characteristics**

Baseline Characteristics	Definition
SVC volume (L) at Screening and Baseline – descriptive statistics	
SVC percent predicted at Screening and Baseline – descriptive statistics	
Baseline SVC percent predicted categories – n (%)	< 50, 50 to < 65, 65 to < 75, 75 to < 85, >=85
Premorbid weight (kg) – descriptive statistics	

Abbreviations: ASL = amyotrophic lateral sclerosis; ALSFRS-R = amyotrophic lateral sclerosis functional rating scale revised; NIV = noninvasive ventilation; PAV = permanent assisted ventilation; SVC = slow vital capacity

**6.1.2. Inclusion/Exclusion Criteria**

The number and percentage of participants not meeting specific inclusion or exclusion criteria will be summarized.

**6.1.3. Protocol Deviations**

All protocol deviations will be listed for all randomized participants. The number and percentage of participants with important protocol deviations for the categories provided in [Table 18](#) will be summarized by treatment group and overall.

**Table 18: Protocol Deviation Categories**

1. Eligibility and entry criteria	6. Visit schedule
2. Investigational product	7. Study procedure/tests
3. Concomitant medication	8. Randomization
4. Informed consent	9. Safety reporting
5. Laboratory assessment	10. Source document
	11. Other

The following protocol deviations will be determined programmatically:

1. Participants who did not take at least 80% of the required treatment doses in RCP
2. Participants who were incorrectly stratified

**6.1.4. Medical and Surgical History**

The medical and surgical history will be summarized by SOC and PT using MedDRA using the latest version in use at the time of analysis. The number and percentage of participants for each category will be reported by treatment group and overall for the FAS.

**6.1.5. Prior and Concomitant Medications / Therapies**

Prior medications are defined as medications with a start date occurring before the first study dose of the RCP. Concomitant medications (RCP) are defined as medications taken during RCP, i.e., either with a stop date after the first study dose of RCP or ongoing during RCP. Concomitant medications (OLE) are defined as medications taken during OLE, i.e., either with a stop date after the first study dose of OLE or ongoing during OLE.

Medications will be coded using the WHODrug Dictionary version in use at the time of the analysis. The number (%) of participants using prior and concomitant medications will be summarized based on the WHO Anatomical Therapeutic Chemical Level 3 Class code and

generic name for FAS. All meningococcal vaccinations and prophylactic antibiotic medications after receiving meningococcal vaccine for subjects who initiated study drug will be listed separately as well.

Nonpharmacologic therapies and procedures will be reported by treatment group and overall for the SS using SOC and PT.

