### 6.5.1.2. ALS-Specific Therapies

There are 2 therapies currently available for treating ALS that may slow disease progression: riluzole and edaravone.

- Patients who are naïve to ALS therapies or have not taken ALS therapies for at least 30 days before screening are allowed to enroll.
- For a patient who is on one or more ALS-specific therapies at Day 1 of the study, the patient must be on a stable dose regimen of riluzole for at least 30 days and/or on a stable treatment of edaravone for at least 60 days (2 treatment cycles) prior to Day 1 and has no plan to discontinue or change dose during the study.
  - Temporary discontinuations or dose modifications of riluzole or edaravone are acceptable at the discretion of the Investigator for medical reasons.
  - Patients receiving edaravone should not receive edaravone infusions on days when study drug is to be administered.
- Patients who do not enter the study on riluzole and/or edaravone will not be permitted to start treatment with either drug during the Randomized Controlled Period. Initiation of riluzole and/or edaravone is permitted during the Open-Label Extension Period.

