**Table 1: Randomization Strata**

Strata	ALS Muscle Weakness at the Onset	Background ALS Therapy (Riluzole or Edaravone) at Study Entry	
	(Bulbar vs. Not)	On Stable Riluzole	On Stable Edaravone
1	Not bulbar	No	Yes, No
2	Not bulbar	Yes	Yes
3	Not bulbar	Yes	No
4	Bulbar	No	Yes, No
5	Bulbar	Yes	Yes
6	Bulbar	Yes	No

a Stable riluzole: at least 30 days on riluzole prior to Day 1.

b Stable edaravone: at least 60 days on edaravone prior to Day 1.

Abbreviations: ALS = amyotrophic lateral sclerosis; vs = versus

Patients who do not enter the study on riluzole and/or edaravone will not be permitted to start treatment with either drug during the RCP.

[figure not shown]
One unblinded interim analysis for futility is planned when approximately 33% of originally planned patients (N = 354) complete the Week 26 visit for the RCP. An independent data monitoring committee (IDMC) will be established to conduct this unblinded interim analysis and periodic review of accumulating data for patient safety and efficacy during the study. Details of the interim analysis methods are described in a separate interim analysis plan (IAP).

**OLE Period:** For each participant, the RCP ends, and the OLE Period starts, when the participant has completed the Week 50 visit assessments and received the first dose for the OLE. Regardless of the randomized assignment, all patients will receive ravulizumab during the OLE Period. Blind to the randomized treatment assignment will be maintained for patients and providers during the OLE Period until the end of the study. Initiation of riluzole and/or edaravone is permitted during the OLE Period. The first dose of the OLE Period will be administered in a blinded fashion to accommodate the loading dose for the patients originally randomized to placebo (see protocol for further details).

The OLE Period will continue for up to 2 years or until ravulizumab is approved and/or available (per country-specific regulations), whichever occurs first.

After the End of Treatment Visit or early discontinuation, patients will be followed for an additional 8 weeks after their last dose of the study drug.

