**Table 5: Definition of TEAEs**

TEAE (RCP)	TEAE (OLE)
For RCP participants entering the OLE, a TEAE will be defined as any AE with onset on or after the first dose of IP in the RCP up to and including the day prior to the first OLE dose.	A TEAE will be defined as any AE with onset on or after first dose of OLE.
For RCP participants not entering the OLE, TEAE will be defined as an AE with onset on or after the first RCP dose of IP.	

If the time of the AE onset is available, it will be used to determine the treatment emergence by comparing with the time of the first study drug infusion, ie, if the AE onset time is prior to the time of infusion, it will not be considered as treatment-emergent.

Abbreviations: AE = adverse event; IP = investigational product; OLE = Open-Label Extension; RCP = Randomized Controlled Period; TEAE = treatment-emergent adverse event

The incidence, toxicity, and relationship to IP will be summarized by the treatment group. Specific AEs will be counted once for each participant for calculating percentages (e.g., overall, SOC, PT). In addition, if the same AE occurs multiple times for a participant, the highest severity and relationship to IP observed will be reported. All TEAEs will be summarized overall and categorized by MedDRA SOC and PT. The ordering of SOC will be alphabetical, and the ordering for PT will be most prevalent (using percentage) PT within each SOC based on the ravulizumab (RCP analysis) or total column (OLE). PTs with the same number of participants (eg, to break ties) will be further sorted by the number of events and then alphabetically.

Table 6 provides an overview of the tabular summaries of AEs for different periods, underlying analysis sets, and treatment group display convention. An “X” in the table represents that an analysis will be performed for the period. For incidence tables, the number of participants and percentage will be tabulated; percentages will be based on the number of participants in the respective treatment groups. For event-rate tables, the rate per 100 patient-years will be calculated as follows (see Table 4 for the definition of patient-years):

$$= 100 \times \frac{\text{Total number of TEAEs for specific reporting period}}{\text{Total Person years for specific reporting period}}$$

The following participant-level listings will be generated for AE data:

- All AEs
- All SAEs
- AEs leading to study drug discontinuation
- AEs leading to death
- AEs of special interest

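### SAP 6.1.5: the date test for RCP concomitant medications has no upper limit on start date, so applied literally it counts drugs both started and stopped in the OLE

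*SAP*

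**What the plan says.** SAP 6.1.5 sorts medications into three groups.

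- Prior: "Prior medications are defined as medications with a start date occurring before the first study dose of the RCP". This is the only start-date criterion in the section.
- RCP concomitant: "Concomitant medications (RCP) are defined as medications taken during RCP", followed by an i.e. clause that gives the test: "either with a stop date after the first study dose of RCP or ongoing during RCP".
- OLE concomitant: the same form of words one period later, with the test "either with a stop date after the first study dose of OLE or ongoing during OLE".

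Prior and concomitant medications are then tabulated as participant counts and percentages by ATC Level 3 class and generic name in the Full Analysis Set. Under SAP 5.1, RCP summaries are shown by arm, ravulizumab and placebo.

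Two other rules bear on the point. Under SAP 1.2, patients not on riluzole or edaravone at entry "will not be permitted to start treatment with either drug during the RCP", whereas "Initiation of riluzole and/or edaravone is permitted during the OLE Period". Protocol 6.5.1.2 agrees: "Initiation of riluzole and/or edaravone is permitted during the Open-Label Extension Period". For adverse events, SAP Table 5 closes the RCP explicitly. For participants who enter the OLE, RCP events are those with onset "up to and including the day prior to the first OLE dose".

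**The concern.** A medication belongs to a period if its use overlaps that period. That requires two conditions: it stopped after the period began, or never stopped, and it started before the period ended. The RCP test states only the first. The OLE test has the same form but does no harm, because no treatment period follows the OLE. The RCP is followed by the OLE, so its test needs the second condition.

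Two things are at stake in the RCP table. First, riluzole or edaravone newly started in the OLE is permitted, but shown as RCP use it would look to a reader like a start that the plan forbids. Second, every OLE participant receives ravulizumab. A drug that a placebo-randomized patient took only in the OLE, while on ravulizumab, would be counted in the RCP placebo column.

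**Working it through.** The plan gives no figure to reproduce. The check applies the stated rule to dates.

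**Inputs.** R = day of first RCP dose = Day 1. E = day of first OLE dose, taken as Day 351, the Week 50 target day in SAP Table 23. S = start day and T = stop day of the medication. The S and T values are illustrative.

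**Rules.**

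- RCP as written: T > R, or no stop date and the drug in use at some time during the RCP (S < E).
- RCP bounded: the rule as written, and also S < E.
- OLE as written: T > E, or no stop date (in all the cases below such a drug is ongoing in the OLE).

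**Results.**

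| Case | S | T | RCP as written | RCP bounded | OLE |
|---|---|---|---|---|---|
| a. Stopped before Day 1 | -60 | -10 | no | no | no |
| b. Started before Day 1, stopped in RCP | -60 | 100 | yes | yes | no |
| c. Started and stopped in RCP | 50 | 100 | yes | yes | no |
| d. Started in RCP, stopped in OLE | 300 | 400 | yes | yes | yes |
| e. Started and stopped in OLE | 365 | 450 | **yes** | **no** | yes |
| f. Started in OLE, still ongoing | 365 | none | no | no | yes |

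Case e is wrong under the rule as written: 450 > 1, so the stop-date branch is met, although 365 > 351 means that no dose fell in the RCP. This does not depend on the dates chosen. If S > E, then T ≥ S > E > R, so T > R always holds. Cases e and f have the same start day and get different RCP classifications only because one drug was later stopped.

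Adding S < E changes case e from yes to no and leaves the other five cases, and every OLE classification, as they were.

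**Does another section supply the bound?** SAP 6.2.2 completes missing or partial medication dates but sets no period limit. Protocol 9.4.4 defines concomitant use as overlap with study drug and does not split it by period. Only Table 5 contains the cut-off, and it governs adverse events.

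**The case against.** The strongest reply is that the sentence begins by restricting the category to drugs taken during the RCP. A drug first taken in the OLE fails that restriction, so a programmer who follows the leading words would exclude case e. This stands. It means the misclassification is not certain; it depends on which half of the sentence is coded. It does not remove the defect. The i.e. clause is offered as the meaning of the leading words and is the only computable criterion given, yet the two halves give opposite answers for case e.

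The second reply concerns consequences, and it also stands. A reader might infer that the rule would generate protocol deviations. The documents do not support that. SAP 6.1.3 derives only two deviations by program, fewer than 80% of required RCP doses and incorrect stratification, and neither uses this classification. Nor does the argument extend to other drug classes. Antibiotics are not on the disallowed list in protocol 6.5.2, and chronic systemic immunosuppressants are restricted there for the whole study, so moving either from OLE to RCP does not turn permitted use into prohibited use.

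A reader might also infer that efficacy results are affected, or that this table is the plan's principal evidence on contamination between arms. The models in SAP 5.3.2, 5.3.3.1.2, 5.4.1.1.2 and 5.4.1.2.2 adjust for baseline covariates and stratification factors, not for this flag. The SAP nowhere gives the table that role.

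**Conclusion.** The concern holds in a limited form. The RCP date test in SAP 6.1.5 is wrong as written and contradicts the definition it explains. Applied literally, it counts every drug both started and stopped in the OLE as RCP use and omits the same OLE start that is still ongoing.

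The size is small. It touches one descriptive table and only participants who entered the OLE, and SAP Appendix 4 describes the OLE data as a small amount. The documents give no count of affected records, so none is offered here. With the study stopped for futility, p-values and confidence intervals are descriptive only (SAP 5.1), and the efficacy analyses do not use the classification in any case.

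The conclusion assumes that the i.e. clause is what gets programmed and that ongoing during RCP means the drug was in use at some time in that period. If a programmer instead used a bare ongoing indicator recorded at study end, case f would be counted too. The same added condition would remove it.

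**What to change.** Add one condition to the RCP rule in SAP 6.1.5: and, for participants entering the OLE, a start date before the first OLE dose. This mirrors Table 5. Participants who never enter the OLE need no bound.

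Leave the rest unchanged:

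- The OLE rule is correct as it stands.
- The missing-date rules in 6.2.2 already set a wholly missing start date to the earlier of first study drug and end of medication, which satisfies the new condition. Medications with both dates missing are already classed there as prior and concomitant.
- The riluzole and edaravone summary in 6.1.5.1 is already limited to the RCP.

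The cost is one clause in the SAP and one condition in the derivation program. Protocol 8.3.7.2 already collects the dates. The change should be made before the table is produced.

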#### **6.1.5.1. Stable Riluzole or Edaravone Use**

The number and percentage of participants will be summarized for the following categories during RCP

- Riluzole use (discontinued versus stable)
- Edaravone use (discontinued versus stable)

Participants will be considered “stable” on the respective medications if not discontinued.

## **6.2. Appendix 2: Technical Specifications for Derived Variables**

### **6.2.1. Derivation of Treatment-emergent Adverse Events for Missing or Incomplete Date of Onset**

If both start and end dates of AEs are completely missing, no imputation will be performed, and those AEs will be considered treatment-emergent.

#### If the start date is partial:

1. If only the day is missing:
  - 1.1. If the month/year of the start date is the same as those of the first study drug administration date, then the missing day will be imputed as the smaller non-missing value of (day of first study drug administration, day of the AE end date).
  - 1.2. Otherwise, impute the missing day as “01”.
2. If both day and month are missing:
  - 2.1. If the year of the AE start date coincides with the year of the first study drug administration date, the partial start date will be set as the first study drug date. If this leads to a date after the AE end date, then the missing day and month of the AE start date will be imputed as the day and month of the AE end date.
  - 2.2. If the year of the AE start date is different from the year of the first study drug administration date, the missing day and month of the AE start date will be imputed as the “01” and “01”.

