### 1.1. Objectives, Estimands and/or Endpoints

Objective	Estimand/Endpoint
Primary	
To evaluate the effect of ravulizumab compared with placebo on amyotrophic lateral sclerosis functional rating scale-revised (ALSFRS-R) score in adult patients with ALS	Estimand: Difference in mean combined assessment of function and survival (CAFS) score between ravulizumab and placebo in the eligible ALS patient population after accounting for the intercurrent event (ICE) of death into the CAFS score calculation using the composite strategy. See Section 5.3 for details.
Secondary	
To evaluate the effect of ravulizumab compared with placebo on ventilation assistance-free survival (VAFS) in adult patients with ALS	Estimand: Hazard ratio (ravulizumab versus placebo) of VAFS event in the eligible ALS patient population using treatment-policy strategy
To evaluate the effect of ravulizumab compared with placebo on respiratory function in adult patients with ALS	Estimand: Difference in mean change in slow vital capacity (SVC) percent predicted score between ravulizumab and placebo at Week 50 in the eligible ALS patient population using treatment-policy strategy
To evaluate the safety of ravulizumab compared with placebo in adult patients with ALS	Endpoint: Incidence of treatment-emergent adverse events (TEAEs), treatment-emergent serious adverse events (TESAEs), and TEAEs leading to study drug discontinuation
To evaluate the effect of ravulizumab compared with placebo on muscle strength in adult patients with ALS	Endpoint: Percent change in combined muscle megascore from Baseline at Week 50 as assessed by handheld dynamometry (HHD)
To evaluate the effect of ravulizumab compared with placebo on neurofilament light chain (NfL) concentrations in adult patients with ALS	Endpoint: NfL concentrations in serum at Week 50
To characterize the pharmacokinetics (PK) of ravulizumab in adult patients with ALS	Endpoint: Change in serum ravulizumab concentration over the study duration
To characterize the pharmacodynamics (PD) of ravulizumab in adult patients with ALS	Endpoint: Change in serum-free complement component 5 (C5) concentration over the study duration
To characterize the immunogenicity of ravulizumab in adult patients with ALS	Endpoint: Presence and titer of anti-drug antibodies (ADAs)

Objective	Estimand/Endpoint
Exploratory	

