### 5.6.2. Adverse Events

AEs will be coded to the corresponding system organ class (SOC) and preferred term (PT) using the latest available version of the MedDRA.

The definitions of TEAE provided in [Table 5](#) will be used to analyze AEs for different study periods. The TEAE (RCP) and TEAE (OLE) represent TEAEs during RCP and OLE, respectively. For handling missing dates of onset, refer to [Section 6.2.1](#). AEs with onset prior to the first administration of study drug will be summarized as pretreatment AEs.

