##### If the start date is partial:

1. If only the day is missing
  - 1.1. If the year coincides with that of the first study drug administration date, then do the following:
  - 1.2. If the month does not coincide with that of the first study drug administration date, then impute the missing day as “01”.
  - 1.3. If the month coincides with that of the first study drug administration date
    - 1.3.1. If the end date is greater than the first study drug administration date, then impute the missing day as the day of the first study drug administration date
    - 1.3.2. If the end date is less than or equal to the first study drug administration date, then impute the missing day as the day of the end date of medication.
  - 1.4. If the year and the month do not coincide with those of the first dose date, then impute the missing day as “01”.
2. If both day and month are missing:
  - 2.1. If the year does not coincide with that of the first study drug administration date, then impute missing month as “01” and missing day as “01”.
  - 2.2. If the year coincides with that of the first study drug administration date
    - 2.2.1. If the end date is greater than the first study drug administration date, then impute the missing day and month as those of the first study drug administration.

2.2.2. If the end date is less than or equal to the first study drug administration date, then impute the missing day and month as those of the end date of the medication.

2.3. If the start date is completely missing, the missing start date will be set as the earlier of the first study drug administration date and end of the medication date.

For meningococcal vaccination, the missing end date will not be imputed.

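### SAP 6.2.1 rule 1.1 compares day-of-month numbers rather than full dates, so some AEs with a missing onset day that outlast the first-dose month are tabulated as pretreatment

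*SAP*

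**What the plan says.** SAP section 6.2.1 handles AEs with incomplete onset dates. Where only the day is missing, rule 1.1 applies under this condition: "If the month/year of the start date is the same as those of the first study drug administration date". The missing day is then "imputed as the smaller non-missing value of (day of first study drug administration, day of the AE end date"). Nothing requires the end date to lie in the same month.

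Other parts of the SAP bear on the result:

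- **Year-only onsets (6.2.1, rule 2.1).** The onset is set to the first-dose date and is changed only under the condition "If this leads to a date after the AE end date". This compares complete dates.
- **Medication start dates (6.2.2, rule 1.3.1).** The matching case reads "If the end date is greater than the first study drug administration date, then impute the missing day as the day" of the first dose. This also compares complete dates.
- **Completely undated AEs (6.2.1).** When start and end are both fully missing, "those AEs will be considered treatment-emergent".
- **Classification (5.6.2).** "AEs with onset prior to the first administration of study drug will be summarized as pretreatment AEs".
- **Endpoint (1.1).** The secondary safety endpoint is "Incidence of treatment-emergent adverse events (TEAEs), treatment-emergent serious adverse events (TESAEs), and TEAEs leading to study drug discontinuation".

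**The concern.** The smaller of two day numbers is the earlier of two dates only when both dates fall in the same month. If the AE ends in a later month, its end date is after the first dose whatever its day number is. Rule 1.1 nevertheless lets a low day number pull the onset back before the first dose, and section 5.6.2 then removes the event from the TEAE tables.

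True onset is unknown for these events and some may really have started before dosing. The fault is that the event is classified by a number unrelated to onset. An AE that resolves early in the following month is dropped, and one that resolves late in that month is kept.

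At stake is the count behind a stated secondary endpoint. The error runs one way, because no AE ending in a later month is wrongly moved into the TEAE tables. The most exposed events are those that begin around the first infusion and resolve within weeks. They would still appear in the AE listings and in the pretreatment or screening summaries.

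**Working it through.** **Inputs.** From the SAP: rule 1.1 (6.2.1), the pretreatment definition (5.6.2), and the full-date comparisons in rule 2.1 (6.2.1) and rule 1.3.1 (6.2.2). The SAP gives no count of partial-date AEs, so there is no figure of its own to reproduce. The calendar dates below are assumed for illustration.

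**Two versions of the rule.**

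- As written: onset day = min(day number of first dose, day number of AE end), placed in the first-dose month.
- Full dates: onset = earlier of (first-dose date, AE end date), or the first-dose date if there is no end date.

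**Step 1: worked cases, with onset recorded as month and year of the first dose.**

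| First dose | AE end | As written | Full dates |
|---|---|---|---|
| 20 Mar | 5 Apr | min(20, 5) = 5: 5 Mar, pretreatment | 20 Mar, TEAE |
| 20 Mar | 25 Apr | min(20, 25) = 20: 20 Mar, TEAE | 20 Mar, TEAE |
| 30 Jan | 28 Feb | min(30, 28) = 28: 28 Jan, pretreatment | 30 Jan, TEAE |
| 20 Mar | 10 Mar | 10 Mar, pretreatment | 10 Mar, pretreatment |
| 20 Mar | none | 20 Mar, TEAE | 20 Mar, TEAE |

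The two versions differ only where the AE ends in a later month and its end day number is below the dose day number. In the first row, the same AE recorded with the year alone would be set to 20 March by rule 2.1 and counted as a TEAE, so the better-documented event is the one that is lost.

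**Step 2: how often.** I took a first dose on each of 365 days from 1 July 2020 and an AE end on each of days 0 to H after dosing, all pairs weighted equally. I counted pairs that end in a later month with end day number < dose day number.

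| H (days) | Set before first dose / ending in a later month | Share | Share of all ends, days 0 to H |
|---|---|---|---|
| 14 | 1,260 / 1,260 | 100% | 23.0% |
| 30 | 5,373 / 5,577 | 96.3% | 47.5% |
| 60 | 10,684 / 16,527 | 64.6% | 48.0% |
| 90 | 15,906 / 27,477 | 57.9% | 47.9% |
| 180 | 31,705 / 60,327 | 52.6% | 48.0% |

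The last column divides the same numerator by all 365 × (H + 1) pairs; for H = 30, 5,373 / 11,315 = 47.5%.

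**Step 3: ends in the first-dose month.** Over all 11,111 pairs of dose date and end date in the same month, the two versions agree every time. The full-date rule therefore changes only AEs that end in a later month.

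**Step 4: missing end day.** Section 6.2.1 sets a missing end day to the last day of the month. Rule 1.1 then misplaces the onset only if the dose day number exceeds that last day. For ends in the month after dosing this happens for 7 of the 365 dose dates (31 Aug, 31 Oct, 29 to 31 Jan, 31 Mar, 31 May), or 1.9%. Over the six months after dosing it is 32 of 365 × 6 = 2,190 pairs, or 1.5%.

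**The case against.** **The word may mean a full date.** Elsewhere the SAP uses it for a point in time, as in Tables 5 and 23. Read that way, rule 1.1 already takes the earlier of two dates. However, rule 2.1 in the same list names the day and the month of the AE end date as separate components, and rule 1.1 fills in a missing day component. The literal reading is the stronger one, and a specification should not depend on the programmer choosing the other.

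**The affected subset is narrow.** This stands. The fault needs a missing onset day, a known onset month equal to the first-dose month, an end in a later month and, in practice, a complete end date (step 4). The number of such AEs is unknown and could be zero. The percentages are shares of evenly weighted calendar pairs within that subset, not of TEAEs. The 100% at 14 days follows automatically, because crossing a month-end within 14 days always gives a lower day number.

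**The convention for undated AEs is not a general default.** Also fair. It covers only AEs with both dates fully missing, and rules 1.2 and 2.2 use the first of the month or of the year. The firmer comparison is with rule 2.1 and the medication rules, which address the same situation with full dates.

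**Consequences are limited.** The study stopped for futility, the safety analyses are descriptive and all AEs are listed. This lowers the stakes, but the TEAE tables remain a main output of the abbreviated report.

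**Conclusion.** The concern holds. Followed as written, rule 1.1 places the onset of some AEs before the first dose because of the day number on which they ended, and no later rule in the SAP resets it. The rule is out of line with rule 2.1 beside it and with the medication rules in 6.2.2, which suggests a drafting slip.

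Within AEs that have a missing onset day in the first-dose month and a complete end date in a later month, about half to nearly all are affected, depending on how soon after dosing they end. That range assumes evenly spread dose and end dates. The effect on the overall TEAE count cannot be stated and may be small. It applies to both arms, and no between-arm bias is shown. The change should be made because the error is one-directional in a stated endpoint and simple to remove.

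**What to change.** Reword rule 1.1 so that, when onset month and year match the first dose, the onset date is the earlier of the first study drug administration date and the AE end date, compared as full dates. If the end date is missing or the AE is ongoing, use the first study drug administration date. This brings the rule into line with rule 2.1 and with section 6.2.2, and it leaves AEs that end in the first-dose month unchanged.

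The cost is one sentence in the SAP and one line of code. If the tables have already been programmed, check whether the code compared day numbers or dates, and list any AE whose classification changes.

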**Table 16: Ethnicity Categories**

Primary (section IV.D of FDA guidance document)	Detailed (section IV.E of FDA guidance document and as recorded on the case report form)
Hispanic or Latino	
 
• Mexican, Mexican American, Chicano/a
 
• Puerto Rican
 
• Cuban
 
• Another Hispanic, Latino/a or Spanish origin
 

Not Hispanic or Latino	Not of Hispanic, Latino/a, or Spanish origin
Not reported	Not reported
Unknown	Unknown

Age, weight, and BMI will be reported based on the most recent data on or before Day 1 (the first study drug infusion).

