**6.2.9. Analysis Windows**

Since the actual study visits for a participant may not exactly coincide with their targeted visit date, the actual visit date will be mapped to the analysis visits as described below.

The analysis visits for the RCP will be derived using prespecified windows around the number of days during the study since the first dose of the study drug (called Day 1). The lower and the upper limits of the analysis windows are described in [Table 23](#).

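### Partial adverse event onset dates are imputed against Day 1 only, so a day-missing onset in the month of the first OLE dose defaults to the RCP and a placebo patient's post-switch event can be shown under placebo

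*SAP*

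**What the plan says.** SAP 5.6.2 defines two kinds of treatment-emergent AE and refers to Section 6.2.1 for missing onset dates in both. Under Table 5, for participants entering the OLE, the RCP window runs from the first RCP dose "up to and including the day prior to the first OLE dose". For the OLE: "A TEAE will be defined as any AE with onset on or after first dose of OLE".

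SAP 6.2.1 handles partial start dates as follows:

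- **Rule 1.1, day missing.** "If the month/year of the start date is the same as those of the first study drug administration date", the day becomes the earlier of the first-dose day and the AE end day.
- **Rule 1.2, day missing, any other month.** "Otherwise, impute the missing day as" 01.
- **Rule 2.1, day and month missing, same year as the first dose.** "the partial start date will be set as the first study drug date", or the AE end date if that is earlier.
- **Rule 2.2, day and month missing.** "If the year of the AE start date is different from the year of the first study drug administration date", the onset becomes 1 January.

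No rule refers to the first OLE dose. The SAP identifies the first study drug dose with Day 1 in 6.2.9 (visit windows count days "since the first dose of the study drug (called Day 1") and again in the note on age, weight and BMI below Table 16. When it means the OLE dose, as in Tables 4 and 5, it says so.

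**The concern.** The RCP/OLE boundary is where placebo patients first receive ravulizumab: Protocol 8.1.4.2 gives them a loading dose at Week 50. At Day 1, rule 1.1 resolves an unknown day toward the dose, so an uncertain event counts as treatment-emergent. At the switch, rule 1.2 resolves it away from the dose. A placebo patient's event that began after the first ravulizumab infusion, recorded with month and year only, would appear in the RCP placebo column and be missing from the Placebo/Ravulizumab column of the OLE tables. SAP version 2 added OLE visit windows (Table 24), but its change table lists no matching change to 6.2.1.

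RCP safety against placebo is a secondary objective, and long-term safety in the OLE is an exploratory one. The SAP retains six OLE tables of treatment-emergent AEs, so a displaced event can affect both sets of output.

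**Working it through.** The documents give no figure to reproduce, so the rules were applied to dates.

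**Inputs.** Rules 1.1 to 2.2 (SAP 6.2.1); the RCP and OLE windows (SAP Table 5); Week 50 at Day 351 ± 3, that is Day 1 + 350 ± 3 days (Protocol Table 1). Assumption: Day 1 may be any date from 1 March 2020 to 31 December 2021. That is 671 dates × 7 switch days = 4,697 pairs.

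**Example.** Day 1 is 10 September 2020, so the first OLE dose is 350 days later, on 26 August 2021. A placebo patient's AE is recorded as August 2021 and ended on 5 September 2021.

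1. August 2021 is not the Day 1 month, so rule 1.1 does not apply.
2. Rule 1.2 gives 1 August 2021.
3. 1 August is before 26 August, so Table 5 makes it an RCP event under placebo, even if it began between 26 and 31 August.
4. Recorded only as 2021, the onset becomes 1 January 2021 under rule 2.2, also RCP.

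**All pairs.**

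| Quantity | Result |
|---|---|
| Switch in the same month and year as Day 1 (rule 1.1 applies) | 0 of 4,697; the gap is 347 to 353 days |
| Switch on the 1st, so day 01 is the dose date and the event is OLE | 3.3% |
| Day 01 falls before the switch, so the event is RCP | 96.7% |
| Share of switch-month days on or after the switch | 51.8% |
| Of those days, share assigned to the RCP | 93.7% |
| Year-only onset in the switch year, assigned to the RCP | 99.9% |

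For year-only onsets, rule 2.1 operates in 2.2% of pairs and rule 2.2 in the rest.

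**Where the rule is right.** Onsets before the switch in the switch month are correctly RCP. In the example that is 25 of 31 days. Day-missing onsets in later months, and year-only onsets in later years, go correctly to the OLE.

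**A branch anchored on the first OLE dose.** For day-missing switch-month events not known to have ended before that dose, none remains in the RCP. If onset were uniform over the month and the end date carried no information, the current rule would misplace 0.518 × 0.937 = 48.5% of switch-month events (true OLE counted as RCP). The new anchor would misplace at most 1 − 0.518 = 48.2% (true RCP counted as OLE). In the example the figures are 6/31 = 19% and 25/31 = 81%. The branch therefore changes the direction of error more than its frequency.

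**The case against.** **The anchor could be read as period-specific.** SAP 6.2.1 does not say that the first study drug dose means the RCP dose. But the SAP equates that dose with Day 1 elsewhere and names the OLE dose when it means it, so a programmer following the text would use Day 1.

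**The rule is blind to treatment.** It also moves early OLE events of Ravulizumab/Ravulizumab patients into the RCP ravulizumab column, and with 2:1 randomization that arm is larger. This stands. A reader might infer that the rule biases the RCP comparison in favor of ravulizumab. The documents do not support that, because both RCP columns can be inflated and no net direction follows. What is specific to the placebo arm is the wrong drug attribution.

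**Not every affected event is post-ravulizumab.** This also stands. A reader might take all day-missing switch-month events in placebo patients to be misattributed, but about 48% of switch-month days precede the switch. Nor are all year-only onsets affected, only those in the switch year.

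**A second anchor trades one error for another.** This stands for day-missing dates and is stronger for year-only dates. In the example, 237 of 365 days (65%) of 2021 precede the dose, which argues against re-anchoring year-only onsets.

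**The effect is small and no decision hangs on it.** The SAP's change table calls the OLE data small. The Week 52 visit follows the switch by two weeks, serious events are reported within 24 hours, the safety analyses are descriptive, and all AEs are listed. These points limit the size of the problem. They do not make the stated rule give the right period.

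**Conclusion.** The gap is real but narrow. As written, SAP 6.2.1 places in the RCP every day-missing onset in the month of the first OLE dose, unless that dose fell on the 1st, and nearly every year-only onset in the switch year. Events in these groups that truly began after the switch are then in the wrong period in both arms, and under the wrong drug in placebo patients.

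The percentages rest on the assumed range of Day 1 dates and on reading the first study drug date as Day 1. The conclusion itself needs only that reading and a switch about 350 days after Day 1. The number of affected events cannot be computed, because the documents do not say how many onset dates are partial; it is expected to be small. The point should be corrected before the final database lock, but it would not be expected to change the trial's conclusions.

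**What to change.** Add a branch to SAP 6.2.1 that mirrors rule 1.1. If only the day is missing, the month and year equal those of the first OLE dose, and the AE end date is missing or on or after that dose, impute the onset as the first OLE dose date and classify the event as treatment-emergent in the OLE. Otherwise keep the current rules.

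For year-only onsets in the switch year, keep the current rule but flag the events in the AE listing. Report, by arm, the number of events whose period depends on the imputation.

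The cost is one rule, one listing flag and one count. The downside is that some events that truly began before the switch will move to the OLE. For placebo patients this errs toward attributing them to ravulizumab, the same direction that rule 1.1 takes at Day 1. For ravulizumab patients, some true RCP events leave the controlled comparison. The count by arm lets a reader judge both.
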